### **5.4 Planned Sample Size and Study Sites**

Planned enrollment is 500 children, adolescents and adults. Patients will be randomized in a 2:2:1 ratio (Ciprofloxacin 0.3% plus Fluocinolone acetonide 0.025% otic solution : Ciprofloxacin 0.3% otic solution : Fluocinolone acetonide 0.025% otic solution), with the aim of including 375 evaluable patients.

Patients will be stratified at enrollment so that approximately 50% of those enrolled will be younger than 18 years old and approximately 50% will be 18 years old and older. It is expected that approximately 80% of enrolled patients will complete the study.

About 50 study sites in US will recruit patients. Enrollment will be competitive, i.e., each study site will continue to enroll patients until recruiting the total of 375 evaluable patients. No study site may enroll more than 50 patients.

## 5.5 Patient Identification and Randomization

Patients will be randomized at Visit 1, after signing informed consent (and assent form, when applicable) and meeting eligibility criteria. A block randomization procedure will be conducted through an Interactive Web Response System (IWRS) which will assign a patient number, which will be used to identify the patient during screening and, if applicable, throughout the duration of the study. Patients who do not meet the inclusion and exclusion criteria will be registered as screen failures through the IWRS.

For patients who have bilateral otitis externa, one ear will be considered the evaluable ear, and it will be randomized to a treatment group. If one ear has a higher total symptom score (as defined in Section Overall Clinical Outcome7.1.1.5) than the other, the ear with the higher score will be the evaluable one. If the symptom score is identical in both ears, the investigator will select the evaluable ear. In either case, the non-evaluable ear will receive the same treatment as the evaluable ear.

Patients will be stratified at enrollment by age group. Age will be classified into 2 groups:

- Younger than 18 years old, and
- 18 years old and older.

It is planned that the total number of patients in the study will be evenly divided between the 2 age groups. Stratification is being performed to ensure adequate representation of each age group in the study and not for statistical considerations.

## 6. STUDY MEDICATION

### 6.1 Identity

#### Investigational Medication

Chemical name	Ciprofloxacin hydrochloride and Fluocinolone acetonide
Generic name	Ciprofloxacin HCl (as 0.3% base) plus Fluocinolone acetonide 0.025% Otic Solution
Trade name	OTOVEL™
Dosage form	Auricular solution, sterile
Manufacturer	████████████████████████████████ for Laboratorios SALVAT, S.A.
Description	Otic solution in single-dose low-density polyethylene (LDPE) blue translucent vials containing 0.25 mL deliverable volume

#### Reference Medication

Generic name	Ciprofloxacin HCl (as 0.3% base) or Fluocinolone acetonide 0.025%
Trade name	Not applicable
Dosage form	Auricular solution, sterile
Manufacturer	████████████████████████████████ for Laboratorios SALVAT, S.A.
Description	Otic solution in single-dose low-density polyethylene (LDPE) blue translucent vials containing 0.25 mL deliverable volume

### 6.2 Administration

Study medication will be self-administered by the patient or administered by the patient's caregiver. At Visit 1, a study staff member will instruct the patient or caregiver in how to open the vials and administer study medication, and will supervise the patient or caregiver during administration of the first dose.

The method of administration for the investigational medication and the comparator medication will be the same: instillation of one vial in the affected ear canal(s) twice a day (approximately every 12h, morning and evening) for 7 consecutive days. Ear wicks or sponges may be used at the Investigator's discretion. Use of ear wicks or sponges must be documented in the EDC.

Study medication will be supplied in single-dose vials containing 0.25 mL deliverable volume per vial. A patient kit will contain 1 pouch of 14 blue translucent vials (2 strips of 7 vials). Patients with bilateral otitis externa will receive 2 kits. The patient or caregiver will administer the contents of 1 vial, twice daily to the affected ear(s) for seven days. The Ciprofloxacin and/or Fluocinolone acetonide dosage will be the same for patients of all ages. Each vial will be an intact unit, and the caregiver will twist off the top of the vial to administer the study medication. The solution should be warmed by holding the vial in the hand for one or two minutes to avoid dizziness which may result from the instillation of a

cold solution. The patient should lie with the affected ear upward, and then the medication should be instilled. The outer ear lobe should then be gently pulled upward and outward. This will allow the ear drops to flow down into the ear canal. This position should be maintained for 1 minute. Repeat, if necessary, for the opposite ear.

The planned maximum exposure to the active ingredient is approximately 1.5 mg of Ciprofloxacin and 0.125 mg of Fluocinolone acetonide per day (approximately 10.5 mg of Ciprofloxacin and 0.875 mg of Fluocinolone acetonide over a 7-day period). This quantity will be twice as much in case of bilateral disease.

### 6.3 Packaging, Labeling, and Storage

The primary packaging of study medication will be performed by [REDACTED], who will supply the investigational medication as pouches, 14 single-dose vials per pouch, as described in Section 6.2. [REDACTED] will send the pouches directly to [REDACTED] [REDACTED]. Each individual vial will contain 0.25 mL deliverable volume of Ciprofloxacin 0.3% and/or Fluocinolone acetonide 0.025% otic. The vial is made from LDPE and is manufactured via a blow-fill-seal process. This process seals the vials directly after manufacture and contains the solution within a unit-dose vial that is intact until the user twists off the cap to administer the medication.

[REDACTED] will serve as the drug distributor to study sites and will label the pouches and cartons ensuring that all study medication kits will be identical in appearance to ensure blinding is adhered to, then pack the kits into boxes, for shipment to each study site that has been approved to receive study medication.

All study medication supplies must be stored in accordance with the manufacturer's instructions (2-25°C or 35.6-77°F). Until dispensed to the patients, study medication will be stored in a secure area, accessible to authorized personnel only.

### 6.4 Blinding and Breaking the Blind

All study medication products (test and comparators) will have the same packaging and labels.

The boxes in which the study medication is packaged, shipped, and dispensed will be identical in appearance. When patients return their used and unused study medication containers to the study site, they will be encouraged to bring them in the original cartons.

Microbiological samples will be processed by a central laboratory under blinded conditions. The central laboratory will be blinded to the treatment assignment of the patient from whom the sample was taken.

Unblinding of study treatment assignment should be an unusual occurrence, and should be done only in case of an emergency when knowledge of the actual treatment becomes medically necessary to affect treatment options. For example, if a patient is worsening, especially if there are worsening systemic signs or symptoms, then, especially because one of the treatment arms does not contain an antibiotic, it may be important to know if treatment with a topical and/or systemic antibiotic might be a reasonable treatment option. The investigator will be able to unblind the study treatment at any time through IWRS.

The treatment unblinding information will be accessible by right-clicking the patient in the "List of patients" tab. A first message will inform the investigator of the unblinding instructions to follow. In order to complete the unblinding process, the following information will be required: the user's password, the patient code concerned by the unblinding request, the patient's birth date and the reason for unblinding.

In this way, the only person unblinded will be the investigator. The investigator should only share this information with people who need to know for the further treatment of the patient and should not be shared with SALVAT or [REDACTED]'s personnel.

#### **6.5 Drug Accountability**

[REDACTED] will provide each Investigator with sufficient amounts of the investigational medication (Ciprofloxacin plus Fluocinolone acetonide otic solution) and the comparator medication (Ciprofloxacin otic solution and Fluocinolone acetonide otic solution). The Investigator will confirm receipt of all kits of study medication using the IWRS and will document receipt in the written study files.

The Investigator will dispense the study medication only to patients included in this study and following the procedures described in this study protocol. Each patient will be given only the study medication carrying his/her number. Each dispensing will be documented in the EDC.

Patients and their caregivers will be asked to keep all used and unused study medication vials, and containers and return them to a study staff member at Visit 3. If patients or caregivers forget to bring in containers at Visit 3, they must bring them in no later than Visit 4.

All supplies must be accounted for at the end of the study. The Investigator is responsible for ensuring that accurate and adequate records are maintained. These records will include lot numbers, quantities received, dates received, dates dispensed, etc., for the investigational medication (Ciprofloxacin and Fluocinolone acetonide otic solution) and the comparator medications (Ciprofloxacin otic solution and Fluocinolone acetonide otic solution). The Investigator must ensure that all used and unused supplies are returned to [REDACTED]. The exact number of vials used in the study must be noted, regardless of whether the study was completed or terminated prematurely. At the time of return, the Investigator must verify that all used and unused supplies of study medication have been returned by the patient and that no remaining supplies are in the patient's possession.

#### **6.6 Compliance**

At Visit 1, the patient or caregiver will be provided with a patient diary and instructed to record each dose of study medication on the diary. At Visit 2, the patient or caregiver will be asked if he or she is using study medication and filling out the patient diary according to directions. Patient diary will be reviewed at Visit 3 to determine study medication compliance as described in Section 10.1.8.

## 6.7 Concomitant Medications

Any medication the patient takes other than the study medication specified in the protocol is considered a concomitant medication. This includes prescribed medications, over-the-counter medications, herbal remedies, vitamins, supplements etc. All treatments must be recorded in the EDC in the concomitant medication page.

At Visit 1, patients will be asked what medications they are currently taking or have taken during the last 30 days. At Visits 2, 3, and 4, patients will be asked what concomitant medications they are currently taking or have taken since the last visit, including medications for pain.

### 6.7.1 Prohibited Concomitant Medications

The following medications will be prohibited during the study (unless the patient has prematurely discontinued study treatment):

- Any investigational drug;
- Any topical or systemic therapy for treatment of otitis externa or otitis media;
- Any systemic antifungal drug;
- Any antibiotic drug other than study medication;
- Any systemic corticosteroid, except nasal or inhaled corticosteroids at stable doses (at least 30 days prior to enrollment)
- Any systemic drug (prescription or over the counter) with anti-inflammatory properties (including biologic response modifiers, nonsteroidal anti-inflammatory drugs such as ibuprofen, naproxen, and cyclooxygenase-2 inhibitors); acetylsalicylic acid for cardiovascular prevention at doses of 325mg per day or less is allowed
- Any compound, agent or substance that is applied to the evaluable external ear or instilled in the evaluable ear canal, other than study medication.

### 6.7.2 Rescue Medication

Concomitant medications will be considered rescue medication if they meet both of the following criteria:

- Any otic or systemic treatment administered for signs/symptoms of otitis externa of the evaluable ear (Note – topical antibiotics applied in the non-evaluable ear are NOT considered to be rescue medication)
- Started after Visit 1 but before End-of-study visit (Note – antibiotics given at or after End-of-study visit are NOT considered rescue medications)

### 6.7.3 Recommended Pain Medication

Patients who are taking anti-inflammatory agents are able to be included in the study, but they must stop the anti-inflammatory treatment (including ibuprofen) at enrolment.

For patients who require analgesic medications for otalgia, the recommended medication is acetaminophen (paracetamol). The use of acetaminophen should never been considered as an initial treatment for otalgia, thus will only be administered after confirming that the study medication is not sufficient for pain relief.

## 7. VARIABLES AND METHODS

### 7.1 Efficacy Parameters

#### 7.1.1 *Clinical Efficacy Parameters*

##### 7.1.1.1 *Brighton grading*

Brighton grading will be assessed in both ears at Visits 1, 3 and 4. For consistency, the same individual should perform the assessments at all 3 visits, if possible. Brighton grading will be assessed as:

- Grade 0: Normal
- Grade I: Tympanic membrane seen. Canal erythematous
- Grade II: Debris in ear canal. Tympanic membrane often obscured by debris.
- Grade III: Edematous ear canal. Tympanic membrane obscured by edematous ear canal. No systemic illness.
- Grade IV: Edematous ear canal. Perichondritis (pinna cellulitis). Systemic illness.

##### 7.1.1.2 *Pain (Otalgia)*

Otalgia in both ears will be assessed at Visits 1, 3, and 4. The investigator will ask the patient (or caregiver if patient is too young) to assess his or her level of pain on the day of the visit. If the patient has taken analgesic medication, he or she will be asked to assess the level of pain before taking the analgesic. For consistency, the assessment of otalgia should always be performed before the ear is examined. Assessments will be on the scale described in Blanch 2000. Otalgia will be assessed as:

- Severe (3) if it interferes with activities of daily living;
- Moderate (2) if it causes discomfort but does not interfere with activities of daily living;
- Mild (1) if there is awareness of pain but not much discomfort
- Absent (0) if there is total absence of pain.

At Visits 3 and 4, pain will be considered resolved if the pain level is 0. Otalgia will be considered improved if the pain level is lower than in the previous visit.

Moreover, patients will complete a diary twice daily in which they will record assessments of ear pain, pain medication use.

Throughout the study, patient or caregiver should record pain severity at least twice daily (prior to dosing). For patients under 7 years old, caregiver will complete the FLACC scale. Patients from 7 years old to younger than 13 years old will record the pain using the Wong Baker Faces Pain Scale. And patients 13 years old and older will record the pain using a VAS scale (see Appendix 3).

#### 7.1.1.3 *Edema*

Edema in both ears will be assessed at Visits 1, 3, and 4 by the investigator. For consistency, the same individual should perform the assessments at all 3 visits, if possible. Edema will be assessed as:

- Severe (3) if the tympanic membrane is not visible because of swelling;
- Moderate (2) if the tympanic membrane is partially visible;
- Mild (1) if there is some swelling but the tympanic membrane is fully visible;
- Absent (0) if there is no visible swelling.

At Visits 3 and 4, edema will be considered resolved if the edema level is 0. Edema will be considered improved if the edema level is lower than in the previous visit.

#### 7.1.1.4 *Otorrhea*

Otorrhea in both ears will be assessed at Visits 1, 3, and 4 by the investigator. For consistency, the same individual should do the assessments at all 3 visits if possible. Otorrhea will be assessed as:

- Severe (3),
- Moderate (2),
- Mild (1),
- Absent (0).

At Visits 3 and 4, otorrhea will be considered resolved if the otorrhea level is 0. Otorrhea will be considered improved if the otorrhea level is lower than in the previous visit.

#### 7.1.1.5 *Overall Clinical Outcome*

Overall Clinical Outcome is based on the Total signs/symptoms score (TSSS), which is calculated by the sum of otalgia score + edema score + otorrhea score. Patients will be allocated to one of the following categories for Overall Clinical Outcome:

1. Clinical Cure: TSSS is 0, as defined in Sections 7.1.1.2, 7.1.1.3 and 7.1.1.4.
2. Clinical Improvement: TSSS is different than 0 but lower than the previous visit, as defined in Sections 7.1.1.2, 7.1.1.3 and 7.1.1.4.
3. Clinical Failure: TSSS does not meet the definitions of Clinical Cure or Clinical Improvement, as defined in Sections 7.1.1.2, 7.1.1.3 and 7.1.1.4.
4. Indeterminate: Discontinued (for reasons other than Clinical Failure) or lost to follow-up.

#### 7.1.1.6 *Time to end of pain*

Time to end of ear pain, defined as the interval (in days) between first dose of study medication and the first day (morning or evening) on which there is no use of analgesics, the diary pain score is zero and the score remains at zero for all subsequent visits until the end of the study.

Patients or caregivers will complete a diary twice daily in which they will record assessments of ear pain and pain medication use, including the time and date of the assessment.

The patient diary information will be used to ascertain the time point (morning or evening) and date at which the ear pain in the evaluable ear ended without use of analgesics.

#### 7.1.2 *Microbiological Efficacy Parameters*

Microbiological cultures of ear discharge will be taken at Visit 1; and in addition at visits 3 and 4 when discharge is present. The otorrhea sample will be taken prior to the debridement of the affected ear(s). A central laboratory will provide microbiological sampling kits with standardized instructions for sample preparation. The entrance to the ear canal will be swabbed with a cotton swab to remove any debris that could cause contamination. The ear canal may be irrigated if that is standard practice at the study site; irrigation must be documented in the EDC. An ACT II Transport Tube, as provided in the microbiological sampling kit, will be gently rubbed against the sides of the ear canal to obtain a suitable specimen for culture. Samples will be shipped to the central laboratory for processing. The central laboratory will be blinded to the treatment assignment of the patient from whom the sample was taken.

The central laboratory will use standardized clinical microbiological laboratory procedures (aerobic cultures only) to identify bacteria by species. Bacterial abundance will be assessed on a scale of 1+ to 4+, per standard laboratory grading (score=0 if the culture is sterile). To be considered a pathogen, the cultured organism must be present at a level of 1+ or higher.

The following species are most likely to be pathogens: *Pseudomonas aeruginosa*, *Staphylococcus aureus*, *Streptococcus* (primarily beta-hemolytic strains), and Gram-negative enteric bacilli (e.g., *Enterobacter*, *Proteus*, and *Klebsiella* species).

The following bacteria are generally colonizers and will not be categorized as pathogens: alpha-hemolytic streptococci, coagulase-negative staphylococci, *Bacillus* species, *Corynebacterium* species, *Lactobacillus* species, and *Propriionobacterium* species. Fungi and yeasts will not be considered as pathogens.

The culture results will be classified in the following groups:

- Negative: culture does not show any growth
- Positive: culture shows microorganism growth
  - Positive with non-pathogens: microorganism are generally colonizers and /or are not categorized as pathogens
  - Positive with pathogens:
    - Target pathogen: *P. aeruginosa* and/or *S. aureus*

- Non-target pathogens: pathogens different to *P. aeruginosa* and/or *S. aureus*

For any patient with a culture positive for a pathogen at Visit 1, bacteriologic response at Visits 3 will be classified as:

- Eradication if the culture does not show growth of any pathogen;
- Presumed Eradication if there is no material to culture and the Overall Clinical Outcome is Clinical Improvement or Clinical Cure as defined in Section 7.1.1.5;
- Persistence if any pathogen cultured at Visit 1 is still present;
- Presumed Persistence if the Overall Clinical Outcome is Clinical Failure but no culture result is available from Visit 3;
- Superinfection if a pathogen not present at Visit 1 is now present (presence of a nonpathogenic organism will not be considered Superinfection); or  
Indeterminate if none of the above definitions are met and the bacteriologic response cannot be determined.

For any patient with a culture positive for a pathogen at Visit 1, bacteriologic response at Visits 4 will be classified as:

- Eradication if the culture does not show growth of any pathogen;
- Presumed Eradication if there is no material to culture and the Overall Clinical Outcome is Clinical Improvement or Clinical Cure as defined in Section 7.1.1.5;
- Persistence if any pathogen cultured at Visit 1 is still present;
- Presumed Persistence if the Overall Clinical Outcome is Clinical Failure but no culture result is available from Visit 4;
- Recurrence if there is reappearance of the pathogen eradicated or presumably eradicated at Visit 3
- Superinfection if a pathogen not present at Visit 1 and Visit 3 is now present (presence of a nonpathogenic organism will not be considered Superinfection);
- Reinfection if there is isolation of a new pathogen different from the one eradicated or presumably eradicated at Visit 3; or
- Indeterminate if none of the above definitions are met and the bacteriologic response cannot be determined.

If Overall Clinical Outcome at Visit 3 is Clinical Failure (whether or not the patient discontinues prematurely) and no bacterial culture is performed at Visit 3, the bacteriologic response at Visit 3 will be Presumed Persistence. If Overall Clinical Outcome at Visit 4 is Clinical Failure and no bacterial culture is performed at Visit 4, the bacteriologic response at Visit 4 will be Presumed Persistence.

Microbiological outcome will be determined for each patient for Visit 3 and for Visit 4 after microbiological culture results are made available to the Sponsor or designee.

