#### **Collection Procedure**

1. Cleanse the area surrounding the infection with a swab containing cleaning solution to remove any contaminating material or flora that may have collected in the ear canal.
2. The ear canal may be irrigated if that is standard practice at the study site.
3. Remove the outer packaging outside of the clean area (always wear gloves). Take the package containing the sterile tube and swab into the clean area.
4. Gently rub against the sides of the ear canal to obtain a suitable specimen for culture. Rotate the swab in the area containing the exudate.
5. After sample collection, remove the A.C.T. ® II cap and quickly insert the swab deep into the agar.
6. Break the swab shaft evenly with the lip of the tube.
7. Replace the cap and quickly tighten to minimize exposure to air.
8. Label appropriately with labels provided in Subject Laboratory Booklet
9. Maintain A.C.T. ® II tube at room temperature.

NOTE: Debridement of the ear is permitted after otorrhea sample collection.

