4.4 Analysis Populations

There will be 6 populations defined for this study: Safety, Clinical intent-to-treat (CITT), Microbiological intent-to-treat (MITT), MITT-PA/SA, CPP, and MPP.

The **Safety population** will include all patients who received any study medication.

The **CITT population** will include all patients who were randomized.

The **MITT population** will include all CITT patients whose Visit 1 microbiological culture yields 1 or more pathogens, as defined in Section 4.7.2.

The **MITT-PA/SA population** will include the pathogen positive subset of the CITT population which includes all patients who received study medication and had culture positive for *P. aeruginosa* and/or *S. aureus* at baseline in the evaluable ear.

The **CPP population** will include all CITT patients who:

- Satisfied all inclusion and exclusion criteria;
- Had analysis results from Visit 1 otorrhea sample;
- Did not receive any prohibited concomitant medications. Note if a patient receives prohibited medication on or after receiving rescue medication and does not have any other major protocol deviations, the patient will be included in the CPP;
- Did not have any other major protocol violations;
- Completed Visit 3 and Visit 4 (unless the patient was deemed a clinical failure at an earlier visit than Visit 4);
- Had compliance rates between 80% and 120% as defined in Section 4.6 (patients who are deemed Clinical Failures are to be included if they had compliance rates between 80% and 120% during the first 3 days of study treatment); and
- Received at least 4 doses of study medication during the first 72 hours.

The **MPP population** will include all CPP patients whose Visit 1 microbiological culture yields 1 or more pathogens and who had microbiological results (when patient has material to culture) from Visit 2 and/or Visit 4 unless the patient was deemed a clinical failure at an earlier visit than Visit 4.

For the CITT, MITT and MITT-PA/SA populations, the treatment group of a patient will be determined by the treatment group to which the patient was randomized.

Effective Date: [REDACTED]
Related to: [REDACTED]

CONFIDENTIAL

Project Document Version No. 2.0
Project Document Effective Date: Date of last signature

Page 12 of 34

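### Sites may irrigate the ear canal before the culture swab is taken, which can make the culture that selects the primary population less sensitive at some sites than at others

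*Protocol*

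**What the plan says.** Protocol Section 7.1.2 describes collection in this order. First, "The entrance to the ear canal will be swabbed with a cotton swab to remove any debris that could cause contamination". Next, "The ear canal may be irrigated if that is standard practice at the study site; irrigation must be documented in the EDC". The transport swab is then rubbed on the canal wall. The same section requires the otorrhea sample to be taken before the ear is debrided.

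Appendix 4 (Collection Procedure) turns this into numbered steps:

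- Step 1: "Cleanse the area surrounding the infection with a swab containing cleaning solution to remove any contaminating material or flora".
- Step 2: "The ear canal may be irrigated if that is standard practice at the study site".
- Step 4: "Gently rub against the sides of the ear canal to obtain a suitable specimen for culture", with the swab rotated where the exudate lies.
- Closing note: debridement is permitted once the sample has been collected.

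The result matters because the SAP's primary population (Section 4.4) is made up of treated patients who "had culture positive for *P. aeruginosa* and/or *S. aureus* at baseline in the evaluable ear". Section 7.1.2 sets the threshold: "To be considered a pathogen, the cultured organism must be present at a level of 1+ or higher". At Visits 3 and 4, a culture that grows no pathogen is classed as Eradication.

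Section 7.1.2 requires irrigation to be recorded. The SAP plans no table, subgroup or sensitivity analysis that uses the record: the subgroups in Section 4.7.1.4 are age and ear wick, and the sensitivity analysis in Section 4.7.1.1 is a complete-case analysis.

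**The concern.** Irrigation puts fluid into the canal and can carry away the material that the swab is meant to sample. The protocol protects the specimen from debridement but not from this step. It leaves the step to local habit at about 50 sites and names no fluid, volume or waiting time. The pre-cleaning is also unsettled. One text has a cotton swab at the canal entrance. The other has a swab carrying an unnamed cleaning solution, applied around the infection.

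Two things are exposed:

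- **Visit 1.** A pathogen washed below the detection threshold reads as negative, and an infected patient leaves MITT and MITT-PA/SA. Those who remain are tilted towards heavier growth and towards sites that do not irrigate.
- **Visits 3 and 4.** Surviving growth that is washed out is recorded as Eradication. This enters the microbiological outcome and sustained microbiological cure. If more pathogens survive without an antibiotic, as one would expect, false Eradication has most room in the fluocinolone arm and would shrink its contrast with the ciprofloxacin-containing arms.

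**Working it through.** **1. Order of steps.** In Appendix 4, irrigation is step 2 and the specimen is step 4. Section 7.1.2 lists the actions in the same sequence. Only debridement is required to come after sampling.

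**2. Can a washed-out Visit 3 culture change the primary endpoint?**

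- A culture is attempted only when discharge is present (Protocol Section 7.1.2; Table 1, footnote c).
- Discharge means an otorrhea score of at least 1, so the total signs/symptoms score (TSSS) is above 0.
- A TSSS above 0 is a therapeutic failure even with a negative culture (Protocol Section 7.1.3; SAP Section 4.7.2).

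Across all combinations of otalgia, edema and otorrhea scores in which a culture would be taken, turning a positive culture negative changes the therapeutic-cure class in 0 cases. The same rule applies at Visit 4. Only the microbiological classifications can move.

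**3. The plan's own sample size.** Inputs from Protocol Section 10.1.1: 62% on ciprofloxacin, a relative increase of 25% (0.62 × 1.25 = 77.5%, given as 78%), two-sided 5%, 80% power, 150 per main arm, and 25% culture-negative at baseline.

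- With 62% versus 77.5% and a continuity correction, the required number is 150 per arm, which matches the plan. Without the correction it is 137.
- Enrolment: 375 / (1 − 0.25) = 500, which also matches.

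**4. Power for the test the SAP names.** SAP Section 4.7.2 specifies Pearson's chi-squared test, so no continuity correction is applied:

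Power = Φ[(d − 1.96·s0) / s1], with d = 0.155, s0 = √(2·p̄·(1 − p̄)/n), p̄ = 0.6975, and s1 = √((0.62·0.38 + 0.775·0.225)/n).

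At n = 150: s0 = 0.05304, s1 = 0.05228, (0.155 − 0.10396)/0.05228 = 0.976, power 83.6%.

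**5. Effect of an assumed loss at baseline.** The documents give no rates. Suppose that 20% to 60% of specimens are irrigated first and that irrigation turns 10% to 30% of positives negative. The share of positives lost is f = (share irrigated) × (share turned negative). Evaluable patients = 500 × 0.75 × (1 − f), and n per main arm = 150 × (1 − f).

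| Assumption | f | Evaluable at 500 enrolled | n per main arm | Power | Enrolment to keep 375: 375 / (0.75 × (1 − f)) |
|---|---|---|---|---|---|
| none lost | 0% | 375 | 150 | 83.6% | 500 |
| 20% × 10% | 2% | 368 | 147 | 82.8% | 511 |
| 40% × 20% | 8% | 345 | 138 | 80.4% | 544 |
| 60% × 30% | 18% | 308 | 123 | 75.7% | 610 |

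The plan counts evaluable patients in MITT. MITT-PA/SA is a subset of MITT, so the numbers per arm in the primary analysis can only be equal or smaller. The table isolates the effect of sampling loss.

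**The case against.** **The primary comparison is not biased.** A reader might infer that washed-out cultures distort the primary treatment effect. The documents do not support that. At Visit 3 the zero-score requirement blocks it. At Visit 1 the sample is taken before the first dose of a double-blind trial, so the loss should be unrelated to arm. The microbiological endpoints that remain exposed are described as supportive only (Protocol Section 10.1.10.2). All of this stands.

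**Evaluable numbers may not fall.** Protocol Section 5.4 has sites enrolling until 375 evaluable patients are reached. On that rule the loss costs recruitment, not power. This stands in part: the same section gives 500 as planned enrolment, and the documents do not say which figure governs if the two diverge.

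**Power may stay adequate.** With the test the SAP names, the middle case keeps power just above 80%. A reader who applied the continuity correction would see a shortfall there, but that correction is not part of the planned test. The assumed rates have no source in the documents, and the 25% culture-negative allowance, taken from earlier studies, may already include some sampling loss.

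**The protocol's safeguards are not broken outright.** Sampling still precedes debridement, which Section 4.1 describes as suction. Sufficient otorrhea is an entry criterion, judged separately from the collection steps. Step 4 presumes that exudate remains, and the detection threshold is low. It would therefore be too strong to say that irrigation defeats those requirements. Entrance cleaning has a legitimate purpose, removing contaminants, and irrigation is the weightier part of the point.

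What survives is the order itself: an optional step that varies by site and comes before the specimen, with a record of it that no analysis uses.

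**Conclusion.** The point holds as a weakness in specimen handling, not as a threat to the validity of the primary comparison. Optional irrigation before the swab, together with two different pre-cleaning instructions, can lower culture sensitivity unevenly across sites.

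- **Visit 1:** truly infected patients can be lost from MITT and MITT-PA/SA, without relation to arm. Under the assumed 2% to 18% loss, keeping 375 evaluable would take 511 to 610 enrolled. If enrolment stops at 500, power falls from 83.6% to between 82.8% and 75.7%, with 80.4% at 8%.
- **Visits 3 and 4:** false Eradication is possible in the microbiological outcome and in sustained microbiological cure only.

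The direction of the effect is reasoned from the procedure. Its size rests entirely on assumed irrigation and wash-out rates.

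**What to change.** - In Section 7.1.2 and Appendix 4, require the culture swab to be taken before any irrigation or other fluid enters the canal, at Visits 1, 3 and 4. In Appendix 4, move step 2 to after specimen collection.
- Use one pre-cleaning description in both places, limited to the outer entrance of the canal.
- For specimens already taken after irrigation, use the existing EDC record in the SAP. Tabulate baseline culture positivity by irrigation status, and repeat the microbiological outcome analyses by irrigation status.
- Do not rely on a primary analysis that leaves out irrigated patients. Those whose pathogen was washed out at baseline are already outside MITT-PA/SA. Dropping the irrigated patients who stayed positive recovers none of them and reduces the sample further.

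The cost is a wording change in the protocol and collection instructions, a short site retraining, and a few added tables. Sites that irrigate routinely change the order of two steps. No new procedure or data item is needed.
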